collection. Electromyographic data will be collected via a Noraxon myoMuscle Ultium EMG (Noraxon USA, INC, Scottsdale, Arizona). Surface EMG data will be visually monitored during the collection of data and sampled.

Following the application of surface electrodes, the reference voluntary contraction normalization method will be utilized so that all surface EMG data can be normalized¹⁶. The reference posture will be a SLR performed to the height of the contralateral knee flexed to 90° with a level to ensure appropriate height is achieved with the moving limb performing max dorsiflexion throughout the motion. Participants will maintain the reference posture for 5 seconds and the middle 3 seconds of the contraction will be selected for data analysis. Two reference voluntary contraction trials will be performed, and the data will be averaged. Participants will be given 30 seconds of rest between each trial. The reference voluntary contraction method was chosen for normalization to account for the knee arthroscopy participants pain and possible weakness¹⁶. Pain and weakness post arthroscopy could hinder obtaining maximal isometric contractions through manual muscle testing. Several studies have shown that within 3 days of knee joint surgery patients can lose up to 80-90% of their quadriceps strength due to a phenomenon called arthrogenic muscle inhibition (AMI) that is in part due to surgical trauma as well as joint effusion^{17,18,19}.

Participants will then have 3 practice repetitions in each position of the foot for a total of 9 repetitions. Upon completion, participants will perform 5 repetitions of SLR and quad sets with the foot in active maximal DF, PF, and a relaxed foot position. In total there will be 15 reps performed. Joint angles will be measured using a goniometer and participants will be instructed to maintain that foot position throughout the motion of the SLR as well as being verbally cued throughout the duration of the task. Video tracking will be used to determine when the motion begins and ends for each repetition. Order of foot positioning and performance of exercises will be randomized. Muscle activation will be recorded for each repetition and 5 repetitions of each foot position will be analyzed. Healthy control participants will perform the exercises on bilateral limbs as will the surgical participants with randomization determining which is done first.

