Participants will place the foot in the desire position prior to the quad set and any motion of the leg and will maintain the foot position throughout the motion of the task. The participant will then perform a quad set holding for 1 second, then raise the leg taking approximately 1 second to raise the leg to the height of the contralateral limb with the knee flexed to 90° (based off goniometric measurements), hold for 1 second at the top and lower during the SLR taking approximately 1 second, then continue to hold the quad set for 1 second with the foot in the specified position while the leg is on the table, then relaxing. During the quadriceps set the participant will actively contract their quadriceps for a maximum total of 5 seconds performing 5 repetitions in each foot positioning and the muscle activation will be recorded. The knee will be extended active maximally as is customary with the performance of a quadriceps set and straight leg raise with the participant in the supine position, and remain extended throughout the task. Participants will be asked to maximally contract their quadriceps for the duration of the task as well. There will be a minimum of 1 second duration during both the concentric and eccentric

phases of the movement. Participants will have a minimum of 60 seconds of rest between each repetition.

Before starting each straight leg raise, a rest period of muscle activity will be recorded with the participants ankle in the respective testing position (active maximal DF, PF, and a relaxed foot position). This will allow for the option for the EMG signal to be rectified and adjusted for baseline noise by subtracting the mean of the rectified signal during the quiet period (before the start of each exercise) from the rectified signal.

Analysis will be performed with the first repetition and the last repetition being omitted and the average of the remaining 3 repetitions will be done for each testing position for both controls and intervention groups.

A video camera will be used to record the performance of each exercise. EMG and video acquisition will be synchronized. Each repetition will be sub-divided in 2 phases: concentric phase defined as when the participant works against gravity to actively lift their leg of eccentric phase defined as when the participant works against gravity to slow down the return to the starting point of the concentric phase.

6 Expected Risks and Benefits

Risks and Discomforts:

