Data will be analyzed using custom-built MATLAB Software. Rectified EMG will be smoothed and filtered according to standard procedures for human surface EMG. Root mean square values will be calculated and normalized to the reference voluntary contraction. Root mean square values will be calculated for each repetition of the SLR and for each of the three phases (isometric, concentric, and eccentric) and across the whole trial. Processed data will be exported to Microsoft Excel and SPSS.

9 Statistical Considerations

Statistical analysis will be performed in excel and SAS Studio (Version 3.8 on SAS 9.4, SAS Institute Inc., Cary, NC). A 2 (group) x 4 (position) x 3 (phase) MANOVA will be performed for each muscle and appropriate post-hoc tests will be used to ascertain differences among variables. The alpha level will be set *a priori* at $p < .05$.

10 Quality Control and Assurance

All protocols will be monitored and analyzed data will be checked for accuracy by the principal investigator and/or a designated research team member. All medical data will be kept in compliance with HIPAA guidelines.

11 Regulatory Requirements

Informed Consent:

The informed consent process will be performed by one of the study investigators or staff. All participants will have the study described to them and will be given as much time as they would like to read an approved, stamped version of the informed consent document. After signing the informed consent document, they will be given a copy for their records. This process will take place at the AREF.

Participant Confidentiality:

Participant confidentiality information is listed above in #7 (Data Management Procedures). All medical data will be recorded and stored in compliance with HIPAA guidelines.

Quadriceps Activation Comparative Analysis Based on Positioning of the Ankle during Supine Straight

Leg Raise.

[name] DPT, SCS, CSCS

Page 7 of 9

12 References

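### Does normalising EMG to a dorsiflexed leg-raise hold with no stated quadriceps effort undermine the group-by-position comparison of Aim 2?

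*Protocol*

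**What the plan says.** Protocol Section 5 defines the reference contraction by posture, height, ankle position and time. "The reference posture will be a SLR performed to the height of the contralateral knee flexed to 90" degrees, checked with a level, "with the moving limb performing max dorsiflexion throughout the motion". On timing: "Participants will maintain the reference posture for 5 seconds and the middle 3 seconds of the contraction will be selected for data analysis". Two trials are averaged. The reason given for a reference contraction rather than a maximal one is that "Pain and weakness post arthroscopy could hinder obtaining maximal isometric contractions through manual muscle testing".

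The test repetitions are straight leg raises and quad sets "with the foot in active maximal DF, PF, and a relaxed foot position". Their height matches the reference. For them an effort level is stated: "Participants will be asked to maximally contract their quadriceps for the duration of the task as well". That sentence follows the description of the test repetitions, so it does not clearly cover the reference hold.

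Section 8 then says: "Root mean square values will be calculated and normalized to the reference voluntary contraction". Section 9 plans a group by position by phase MANOVA for each muscle at the 5% level. Section 1 states the hypothesis as a percentage of the reference contraction. Aim 2 in Section 2 asks whether the position effect differs between healthy and post-operative participants, which is the group-by-position term.

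**The concern.** The divisor is a contraction whose quadriceps effort is left open. Holding the leg at the set height can be done with whatever effort the limb needs, or with much more. Section 5 itself describes pain, weakness and inhibition after knee surgery, so the two groups could plausibly hold the reference at different efforts.

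If they do, and nothing else differs, every %RVC value in the surgical group is multiplied by a constant, and so is the difference between ankle positions. The Aim 2 test could then report a group difference in the position effect that is only a difference in the divisor, or hide a real one. Ratios between positions within a limb do not involve the divisor, so moving the MANOVA to a log scale looks like an inexpensive cure.

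**Working it through.** **Inputs.** From the Protocol: 50 participants per group (Section 4), two reference trials averaged and three test repetitions averaged (Section 5), alpha 0.05 (Section 9). The Protocol gives no SD, effect size, power or %RVC value, so there is no figure to reproduce. That the reference is taken on the tested limb is inferred. All other inputs are assumptions: between-person log-SD 0.5, trial CV 10%, PF/DF 0.80 and relaxed/DF 0.85 with person SD 0.2, reference-effort log-SD 0.2, three phases.

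**Algebra.** Let g be the limb's electrode gain, e_t test effort and e_r reference effort. The reference is g·e_r.

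- Position proportional, test EMG = g·e_t·p: the DF−PF contrast is 100·(e_t/e_r)·(p_DF − p_PF), and the PF/DF ratio is p_PF/p_DF. The additive contrast depends on the test-to-reference effort ratio; the ratio depends on neither effort.
- Position a fixed amount, test EMG = g·(e_t − s), with s = 0 in DF: the contrast is 100·s_PF/e_r, and the PF/DF ratio is (e_t − s_PF)/e_t. The additive contrast depends on e_r only; the ratio depends on e_t only.

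**Numbers.** Set healthy e_t = e_r = 1, p_PF = 0.80 or s_PF = 0.20. The healthy contrast is 20 %RVC points and the healthy PF/DF ratio 0.80 under either form. Put the surgical deficit at ×0.77:

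- reference lower, either form unless the test falls proportionally with it: 100 × 0.20/0.77 = 26.0 points
- test lower, proportional: 100 × 0.77 × 0.20 = 15.4 points
- test lower, fixed amount: ratio (0.77 − 0.20)/0.77 = 0.74

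Simulated rejection of group by position, with no true difference in p or s, used a two-sample Hotelling T² on DF−PF and DF−relaxed averaged over phases (3,000 runs; 1,500 for the two rows with both efforts lower):

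| Surgical ×0.77 applied to | Position acts | DF−PF, surgical v healthy | PF/DF, surgical v healthy | %RVC rejects | log rejects |
|---|---|---|---|---|---|
| reference only | proportionally | 26.0 v 20 | 0.80 v 0.80 | 24.8% | 5.3% |
| reference only | by fixed amount | 26.0 v 20 | 0.80 v 0.80 | 29.0% | 4.7% |
| test only | proportionally | 15.4 v 20 | 0.80 v 0.80 | 25.4% | 4.7% |
| test only | by fixed amount | 20 v 20 | 0.74 v 0.80 | 5.0% | 49.3% |
| both | proportionally | 20 v 20 | 0.80 v 0.80 | 5.4% | 5.3% |
| both | by fixed amount | 26.0 v 20 | 0.74 v 0.80 | 34.5% | 51.3% |

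With equal effort both scales reject 4.2 to 5.1%. Repeat runs of the reference-only rows gave up to about 33% on %RVC.

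**Reading the table.**

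1. A group difference in reference effort is not in itself the trigger. When both efforts fall together and position is proportional, both scales keep their size. A second simulation with different assumptions (healthy activation 0.60/0.50/0.50, reference 0.40) agrees: a common factor of 0.8, 0.6 or 0.5 gives 5.0%, 4.6% and 4.9% on %RVC.
2. The log scale keeps its size in four of the six rows and %RVC in two. The log advantage comes from the two reference-only rows. In the other four, each scale holds in two.
3. The reference-only pattern is the one that Section 5 supports least. The pain and weakness described there hinder maximal contractions, and the test task, not the reference, is the maximal one.

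**The log alternative in detail.** For within-limb terms log(RMS) and log(%RVC) are the same test, because one reference per limb and muscle cancels. For the group main effect they are not: under a common ×0.77 deficit with proportional position effects, it rejects 71% on log(RMS) and 5.5% on log(%RVC). Running the whole MANOVA on log(RMS) would drop the between-person normalisation that Section 8 requires.

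**The case for a change.** The strongest case for a change is that an effort cue is a procedure, not an analysis detail. It has to be settled before data collection, and no analysis plan can restore it afterwards. Writing it down costs one sentence. The distortion is also potentially large. With only the surgical reference lower, by 10/23/38%, false rejection on %RVC is 7.2/24.8/65.7% (proportional). With true surgical ratios 10% higher, power on %RVC falls from 73.8% with equal references to 58.9/36.4/14.8%, while log stays at 79 to 81%.

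The algebra stands, and so do those figures under their assumptions. A written cue would be good practice. Three things limit the force of the argument:

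- The hold is already constrained by height, knee and ankle position, and time, and is described once for all participants. Nothing suggests a different instruction by group. Staff giving one spoken cue to everyone is the ordinary way to fill this gap.
- The within-limb ratios that avoid the divisor remain available. Section 5 keeps the electrodes in place throughout, so ratios can be computed from the stored RMS without the reference. Reference RMS by group can also be tabulated, although raw amplitude is only a rough guide between people.
- The sizes rest wholly on assumed inputs. At a 23% lower reference, varying the position ratios and their SD moves false rejection on %RVC from 5% to 92%. In the second simulation (reference 0.30 v 0.40) within-person log-SD alone moves it from 88% to 9%.

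Section 9 names four positions where Section 5 tests three. That mismatch is a separate matter and does not alter this one: with four positions the %RVC figure at ×0.77 is 22 to 26%.

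**Conclusion.** No change to the plan follows. The additive %RVC test for Aim 2 is sensitive to effort, but the condition is narrower than it first appears. With proportional position effects, what matters is a group difference in the ratio of test to reference effort. With fixed-amount effects, a difference in reference effort distorts %RVC and a difference in test effort distorts the log scale. The Protocol shows neither a group difference in effort nor the form of the position effect.

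At a 23% deficit the error is about 25 to 35% on %RVC in the cases that harm it, and about 50% on the log scale in the cases that harm that one, all under assumed variances. Choosing between them is choosing the scale on which an interaction is defined. The Protocol has made that choice openly by stating its hypothesis in %RVC, for a sound reason. Transformations and supporting analyses are commonly left to an analysis plan, which is not at hand here. What remains is an unwritten effort cue for an otherwise standardised hold: a missing detail that those running the sessions can fill, not an error in the design.

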The risks of this study are minimal but do include quadriceps fatigue and gastrocnemius/soleus as well as tibialis anterior muscle fatigue. To minimize muscle soreness and fatigue, adequate rest breaks will be utilized between sets of contractions. The exercise is strictly designed to keep heart rates normal and measure strength of the quadriceps contraction. The appeal of this exercise regimen is that it is not strenuous and can be used during the first rehabilitation day after surgery while at the same time eliciting changes in quadriceps activation that can be used for proper instruction by therapists and trainers to their patients for optimal rehabilitation. This exercise is designed to keep heart rates in normal exercise ranges. There is a slight risk of temporary skin irritation occurring when the surface EMG electrodes are removed from the skin. The skin may appear to be red after the electrodes are removed.

Benefits:

No direct benefits are expected for the participants involved in the study, however results from the study should help clinicians better understand the current cutting edge in exercise technology.

7 Data Management Procedures

All personal information is strictly confidential and no names will be disclosed except as required by law. Data sheets will have names and identifying information replaced with a participant code to protect the confidentiality of the participant. All information provided by the

participant during this project will be recorded on the appropriate forms and stored in a locked room in the Andrews Research & Education Foundation (AREF) research facility. In addition, all participant data forms will be scanned and stored, along with summary information forms, spreadsheets, and photos, in a secure password protected folder on a laptop in which only study investigators will have access to and will be permanently deleted following any and all publications or presentations have been completed related to this research. All records related to this research will be retained in a secure location for a period of 3 years following the completion of all study related activities, at which time they will be properly destroyed.

8 Data Analysis

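### Foot-position order is randomised, but the model named in Section 9 has no period term, so any drift during the session costs precision in both aims

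*Protocol*

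**What the plan says.** Section 5 (Study Design and Procedures) sets the task: "participants will perform 5 repetitions of SLR and quad sets with the foot in active maximal DF, PF, and a relaxed foot position". On sequence it says only "Order of foot positioning and performance of exercises will be randomized", and on limbs "Healthy control participants will perform the exercises on bilateral limbs as will the surgical participants with randomization determining which is done first". It gives no unit of randomisation, no balancing scheme and no rule for recording the order used. Section 4 matches controls to surgical participants on age and leg tested, and order is not a matching variable.

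Normalisation comes before practice and testing: "Two reference voluntary contraction trials will be performed, and the data will be averaged". No later reference contraction is described.

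On effort, Section 5 says "Participants will be asked to maximally contract their quadriceps for the duration of the task as well". Section 6 says "The risks of this study are minimal but do include quadriceps fatigue and gastrocnemius/soleus as well as tibialis anterior muscle fatigue". Against this, Section 5 requires at least 60 s of rest between repetitions, Section 6 promises rest breaks to limit fatigue, and participants avoid tiring activity for 24 hours beforehand.

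The analysis in Section 9 is: "A 2 (group) x 4 (position) x 3 (phase) MANOVA will be performed for each muscle". No period, order or limb-order term is named.

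**The concern.** Each participant serves as his or her own control for foot position, so the design is in effect a crossover of three positions within one session. In such a design, whatever changes over the session is superimposed on the position effect. Fatigue could move the EMG amplitude one way and learning the other. Because the reference is taken at the start, every later value carries whatever drift has built up since.

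Randomising the order stops this drift from favouring one position systematically. It does not remove it. For one participant the dorsiflexion block comes first and for another last, so their contrasts differ for a reason unrelated to the ankle. A model with group, position and phase alone leaves that difference in the error term. What is at stake is the precision of Aim 1 (position contrasts) and Aim 2 (whether those contrasts differ between groups).

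**Working it through.** **Nothing to reproduce.** The protocol plans 50 participants per group and gives no effect size, SD, drift or power. The calculation is therefore scale-free.

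**Inputs from the protocol**
- Three tested positions with five repetitions each, 3 × 5 = 15, which agrees with "In total there will be 15 reps performed". Section 9 counts four positions; that mismatch is a separate matter, and the three that are performed are used here.
- 50 participants per group; α = 0.05.

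**Assumptions**
- The five repetitions of a position are done together as a block. Section 5 does not say so outright.
- Drift is linear, *d* per block, and additive.
- *s* is the SD of a within-person contrast between two positions without drift.
- Order is randomised independently for each participant, and the test is two-sided.
- The effect is one that gives 80% power when there is no drift.

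**Step 1: variance added by order.** Three positions have 6 orders. The gap in block number between two given positions is ±1 in 4 orders and ±2 in 2 orders. Its mean is 0 and its variance is (4 × 1 + 2 × 4) / 6 = 2. Each participant's contrast therefore has variance s² + 2d², an inflation of 1 + 2(d/s)².

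Omitting the first and last of the five repetitions does not change this. Repetitions 2, 3 and 4 have the same centre as repetitions 1 to 5, so the gap between blocks is the same.

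**Step 2: loss of power.** Power = Φ(2.802 / √inflation − 1.960), where 2.802 = 1.960 + 0.842.

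| d/s | Inflation | Ratio of standard errors | Power | n per group to regain 80% |
|---|---|---|---|---|
| 0.1 | 1.02 | 1.01 | 79% | 50 × 1.02 = 51 |
| 0.25 | 1.125 | 1.06 | 75% | 50 × 1.125 = 56.25, so 57 |
| 0.5 | 1.5 | 1.22 | 63% | 50 × 1.5 = 75 |

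The inflation is the same for both aims when the groups drift alike, so the loss of power applies to both. The last column concerns the two-group contrast of Aim 2.

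**Step 3: is there bias in Aim 2?** The contrast was simulated with no true group difference (6,000 runs per setting, 50 per group, independent simple randomisation of order, no period term).
- Equal drift, d/s = 0.25: type I error 5.1%.
- Equal drift, d/s = 0.5: 5.3%.
- Unequal drift, 0.5 in one group and 0.1 in the other: 4.9%.
- Unequal drift, 1.0 and 0.2: 5.2%.

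The mean estimate was near 0 in every setting.

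**Step 4: which remedy restores power?** Aim 2, d/s = 0.5 in both groups, simulated. The order term was the block-number gap, with its slope fitted separately in each group.

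| Order allocation | Order term in model | Power |
|---|---|---|
| Simple randomisation | no | 62% |
| Shared within matched pairs, analysed as independent groups | no | 64% |
| Balanced within each group | no | 64% |
| Simple randomisation | yes | 79% |
| Balanced within each group | yes | 79% |

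Balancing without the term makes the test conservative (type I error about 1.7%), because the design removes the order variance from the estimate while the analysis still counts it as error.

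**The case against.** Four arguments stand against the point.

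**The drift may be small.** Rest of at least 60 s after a contraction of about 5 s, the promised rest breaks and the 24-hour restriction all limit fatigue. At d/s = 0.1 the loss is about one percentage point. This stands: nothing in the protocol shows that drift is material, and the larger figures are conditional.

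**Randomised order already protects the comparison.** It does so against bias, and this part stands in full. A reader might infer that fatigue could imitate an Aim 2 difference, especially if surgical limbs tire faster or the orders happen to differ between groups. The protocol does not support that. Under per-participant randomisation the expected order gap is zero in each group whatever its drift. The chance shift in the between-group contrast has SD d × √(2 × 2 / 50) = 0.28d, and its square, 4d²/50, is exactly the extra term in the variance 2(s² + 2d²)/50. The ordinary standard error already covers it. A false-positive rate above the nominal level would need orders drawn by group or session. The protocol does not say this, although it does not state the unit either.

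**Limb order is irrelevant to position.** Under additive drift this is right. Testing a limb second adds the same amount to all three positions on that limb, so it cancels from the position contrasts.

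**A period term is ordinary analysis-plan detail.** In part. A plan that is not shown may add it. But the protocol itself names the model, and the method of allocating orders has to be set before testing, which no later analysis plan can do.

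**Conclusion.** The point holds as one of precision. The model as written in Section 9 leaves any session drift in the error of the position contrasts (Aim 1) and of the group-by-position contrast (Aim 2). This can hide a difference. It does not bias Aim 2 and does not raise the type I error when order is randomised per participant.

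The size is unknown, because the documents give neither drift nor SD. Under linear drift between blocks, 80% power becomes about 79%, 75% or 63% at d/s of 0.1, 0.25 or 0.5, and the rest periods may keep the trial near the first figure. At 0.5, a period term recovers nearly all of the loss (from about 62% to 79% in simulation). The figures also assume that positions are done in blocks and compared within person. This is a nearly free improvement, not an error that undermines the trial.

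**What to change.** 1. In Section 5, state that order is randomised separately for each participant and whether each position's repetitions are done as one block. Allocate the six orders of the three tested positions in balanced blocks within each group. With 50 per group this gives four orders used 8 times and two used 9 times (4 × 8 + 2 × 9 = 50); draw at random which two are used 9 times.
2. Record the order actually used for every participant.
3. In Section 9, replace or supplement the named analysis with a within-person (mixed) model that includes period. Period-by-group can be added if the groups are expected to drift at different rates.
4. Optional: share orders within matched pairs and model limb order. Neither is needed for the gain shown above.

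If only one change is made, it should be the period term, supported by the recorded order.

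Cost: a randomisation list and a few degrees of freedom (two for period with three blocks, two more for period-by-group). No extra procedures or participants are needed.
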